4. STUDY DESIGN

4.1 General Design

This is a Phase 3, pivotal, confirmatory, 1:1 randomized, double-blind, placebo-controlled, parallel group study to evaluate the efficacy and safety of izokibep in subjects with moderate to severe HS. Subjects must have HS lesions present in ≥ 2 distinct anatomic areas, 1 of which must be Hurley Stage II or Hurley Stage III, and a total AN count (total sum of abscesses and inflammatory nodules) of ≥ 5 . Subjects with draining fistula count of > 20 at screening or Day 1 will be excluded.

Overall, 250 subjects (125 subjects per treatment group) with moderate to severe HS are planned to be enrolled at sites globally in North America, Europe, and Asia Pacific. Additional sites and regions may be added.

Subjects meeting eligibility criteria will be randomized into 1 of 2 treatment groups in a 1:1 ratio as follows:

- Group 1 (n = 125): placebo every week (QW) from Day 1 through Week 15, then izokibep 160 mg QW from Weeks 16 to 51.
- Group 2 (n = 125): izokibep 160 mg QW from Day 1 through Week 51.

[figure not shown]
The first dose of study drug (i.e., izokibep or placebo) will be administered on Day 1.

Randomization will be stratified by prior TNFi use for HS (Yes/No) and Hurley Stage (II or III). Subjects enrolled with stable concomitant antibiotic use (dosing regimen has been stable for ≥ 4 weeks prior to first dose of study drug) will be capped at approximately 30%.

The maximum planned length of participation in the study for an individual subject is up to 63 weeks, which includes the following:

- Screening Period of up to 28 days (4 weeks)
- Treatment Period of 51 weeks
- Follow-up visit at 8 weeks after the last dose of study drug.

Figure 1: Study Design Schema

EOS = end of study; EOT = end of treatment; QW = every week

^aRandomization will be stratified by any prior TNFi use for hidradenitis suppurativa (Yes/No) and Hurley Stage (II or III).

^bSubjects in Group 1 (placebo QW) will receive placebo QW until Week 15, then izokibep QW beginning at Week 16 until Week 51. Subjects in Group 2 (izokibep QW) will receive izokibep QW.

^cAn 'end of treatment visit' will be conducted at Week 52 (± 5 days). A 'safety follow-up visit' will be conducted at Week 59 (± 5 days). For subjects who early terminate, the end of treatment visit should be completed 1 week after the last dose of study drug and safety follow-up visit completed 8 weeks after the last dose of study drug (± 5 days), where possible.

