6.8 Secondary Efficacy Endpoints

The secondary efficacy endpoints are defined in [Table 4](#):

Table 4: Secondary Efficacy Endpoints

Endpoint	Derivation
HiSCR90 at Week 12	At least 90% reduction from baseline in the total AN count, with no increase from baseline in abscess or draining fistula count at Week 12. Must meet all 3

	criteria as described for the primary endpoint replacing 75% with 90%
HiSCR100 at Week 12	At least 100% reduction from baseline in the total AN count, with no increase from baseline in abscess or draining fistula count at Week 12. Must meet all 3 criteria as described for the primary endpoint replacing 75% with 100%
HiSCR50 at Week 12	At least 50% reduction from baseline in the total AN count, with no increase from baseline in abscess or draining fistula count at Week 12. Must meet all 3 criteria as described for the primary endpoint replacing 75% with 50%
HS Flares Through Week 12	
$\geq 25\%$ increase in AN count with a minimum increase of 2 AN relative to baseline, i.e. subject must meet all the following criteria at Week 12:
 
 • $(\text{AN count at current visit} - \text{AN count at baseline}) / \text{AN count at baseline} \times 100\% \geq 25\%$ • $\text{AN count at current visit} - \text{AN count at baseline} \geq 2$ 
A subject will be counted as having HS flare if they have a HS flare at any assessment after baseline, up to and including the assessment at Week 12 (including scheduled and unscheduled visits and early termination visits)

Change in DLQI from baseline to Week 12	(DLQI score at current visit – DLQI score at baseline) at each post baseline visit until Week 12 DLQI comprises 10 items arranged in 6 categories: symptoms and feelings (questions 1 and 2), daily activity (3 and 4), leisure (5 and 6), work or study (7), interpersonal relationships (8 and 9), and treatment (10). The total score can vary from 0 (no impact) to 30 (maximum impact).
AN count of 0, 1, or 2 at Week 12	Observed values of 0,1, or 2 for AN count (abscess count + inflammatory nodule count)

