9.5 Analysis of Primary Efficacy Endpoint

The primary efficacy variable is defined as HiSCR75 at Week 12.

The statistical null and alternative hypotheses to be used to assess the primary objective are:

$$H_0: \pi_{ABY} - \pi_{PBO} = 0$$

$$H_A: \pi_{ABY} - \pi_{PBO} \neq 0$$

where π_{ABY} and π_{PBO} are the proportion of subjects achieving HiSCR75 at Week 12 among subjects randomly assigned to receive izokibep and placebo, respectively.

The treatment policy strategy approach for the estimand will be used in general, so subjects will be included using observed data at Week 12 regardless of treatment compliance, use of rescue medications or procedures except as noted below, or any other protocol deviations.

Subjects who receive antibiotic therapy that could affect HS will be included in the primary analysis by imputing as non-responders (non-response imputation or NRI) at subsequent timepoints. A list of all oral antibiotic therapy that results in such imputation will be finalized after review of all oral antibiotic therapy received by any subject and before unblinding of the study, and will include tetracycline, clindamycin, and possibly other products. Similarly, subjects with missing HiSCR75 assessments at Week 12 due to discontinuing treatment due to an AE or lack of efficacy will also be imputed as NRI. These subjects will be identified by meeting any of the following criteria:

- Subject has adverse event with action taken = “Drug Withdrawn” and corresponding AE start date is before study day 84 and last dose of study drug is taken before study day 84 or
- Subject has last dose of study drug taken before study day 84 and reason for discontinuation of treatment is any of the following:
 - Adverse event
 - Death
 - Lack of efficacy
 - Disease progression

Other subjects with missing data will have efficacy data imputed using multiple imputation, as follows:

Multiple imputation will be implemented to replace missing endpoint data using multiple draws from a posterior predictive distribution estimated from the placebo group only. First, a monotone missingness pattern will be enforced using Markov Chain Monte Carlo (MCMC). The MCMC process will use predictor variables of:

- baseline abscess count (continuous)
- baseline inflammatory nodule count (continuous)
- baseline draining fistula count (continuous)
- age (continuous)
- baseline BMI (continuous)

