A stratified test of response rates will be used for the primary analysis. Within each of the 4 strata used for randomization, the response rate for each treatment group and corresponding standard error will be calculated. The difference in response rates (risk difference) will be calculated for each stratum. The common risk difference among the 4 strata and associated standard error will be estimated by combining the observed risk differences using Cochran-Mantel-Haenszel weighting. The estimated risk difference divided by the standard error will be used as the test statistic and a p-value calculated assuming that the test statistic follows a standard normal distribution under the null hypothesis. Analyses at earlier timepoints when data to calculate the HiSCR75 are collected will also be presented using the same methodology. P-values from earlier timepoints and Week 16 will be presented for descriptive purposes, not part of the alpha-preserving multiple testing strategy.

Sample SAS code with stratification factors of comparing each dosing regimen of izokibep to the combined placebo group is given as following:

```
ods output commonpdiff = ;
proc freq data= ;
  tables stratum * treatment * response / cmh commonriskdiff (test=mh cl=mh);
  weight count / zeros;
run;
```

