Subjects who have missing data at Week 12 due to discontinuation of treatment due to adverse event or lack of efficacy or who received an oral antibiotic that could impact HS will be included in the analysis with NRI (did not achieve AN count of 0, 1, or 2). Other missing data will be handled using multiple imputation analogously to the primary endpoint. Only subjects with Hurley Stage II at baseline will be included in the hypothesis test for AN count, while other subjects will be summarized, and a p-value reported for descriptive use only.

Hurley stage collected in the eCRF ('worst case' Hurley stage from the baseline Lesion Counts eCRF page) will be used.

Methodology will be identical to that used for the primary endpoint with the exception of stratification factors. For the secondary endpoint, achieve AN count of 0, 1, or 2 at Week 12, which uses only subjects with Hurley Stage II at baseline, the stratification factor of baseline Hurley Stage will be omitted from the analysis. For the analysis using all subjects, the stratification factor of baseline Hurley Stage will be used, as in the primary endpoint analysis.

9.6.4 NRS of Skin Pain at Week 12

The secondary endpoint of percentage of subjects achieving at least 3 points reduction from baseline in NRS in Patient Global Assessment of Skin Pain at its worst at Week 12 among participants with baseline NRS ≥ 3 will be analyzed analogously to the primary endpoint.

The number and proportion of subjects achieving at least 3 points reduction from baseline in NRS in Patient Global Assessment of Skin Pain at its worst at Week 12 among participants with baseline NRS ≥ 4 in each treatment group will be reported.

Subjects who have missing data at Week 12 due to discontinuation of treatment due to adverse event or lack of efficacy will be included in the analysis with NRI (did not achieve least 3 points reduction from baseline in NRS in Patient Global Assessment of Skin Pain at its worst). If a subject received certain prohibited analgesic therapy within 28 days of the visit (including the day of the visit) for HS indication, then the visit within the 28 days of the start date of the prohibited analgesic will be imputed as NRI.

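### The AN 0-2 endpoint in Hurley II subjects depends on baseline AN count by construction, but its treatment comparison adjusts only for prior TNFi use; the test is valid and what is lost is precision.

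*SAP*

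**What the plan says.** SAP Table 4 (section 6.8) defines the endpoint as "Observed values of 0,1, or 2 for AN count (abscess count + inflammatory nodule count"), with no reference to the subject's starting count. Entry requires "a total AN count (total sum of abscesses and inflammatory nodules) of ≥ 5" (SAP 4.1), and no upper limit on AN count is stated.

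For the test, SAP 9.6.3 says "Only subjects with Hurley Stage II at baseline will be included in the hypothesis test for AN count" and "Methodology will be identical to that used for the primary endpoint with the exception of stratification factors". In this subset "the stratification factor of baseline Hurley Stage will be omitted from the analysis". The primary method (SAP 9.5) calculates a risk difference within each stratum and obtains a common estimate by "combining the observed risk differences using Cochran-Mantel-Haenszel weighting". The randomisation factors are prior TNFi use and Hurley Stage (SAP 4.1), so only prior TNFi use remains. AN count is not a randomisation factor.

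Baseline AN count is collected and summarised (SAP 6.5 and 9.3). Baseline abscess and inflammatory nodule counts are predictors in the imputation model (SAP 9.5), but they do not enter the treatment comparison. For continuous endpoints, SAP 8.2 does adjust each repeated-measures model for the baseline of its own response. Sensitivity and subgroup analyses are dropped (SAP 8.8, 9.5.1 and 9.11), so no other analysis fills the gap.

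**The concern.** HiSCR is measured against each subject's own baseline, and this endpoint is not. A subject who enters with 5 lesions must lose 3; one who enters with 30 must lose 28. Applying the HiSCR method unchanged leaves unused the baseline variable that bears most directly on this outcome, in a subset smaller than the trial.

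What is at stake is the width of the confidence interval and the power of one secondary test. The endpoint is fifth in the SAP 8.6 sequence (sixth in protocol 9.1.1). It is reached only if the primary and four secondary tests succeed, and in the SAP order only the pain and flare tests follow it.

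**Working it through.** **The plan's only power figure.** It concerns HiSCR75, not AN 0-2: 125 per arm, 15% v 35%, 2-sided alpha 0.05, unstratified (SAP 4.4). With mean rate 0.25:

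- null SE = √(2 × 0.25 × 0.75 / 125) = 0.0548
- alternative SE = √((0.15 × 0.85 + 0.35 × 0.65) / 125) = 0.0533
- power = Φ((0.20 − 1.96 × 0.0548) / 0.0533) = Φ(1.74) = 95.9%

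The stated figure of about 95% is reproduced. No power is stated for AN 0-2.

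**Reduction needed.** To reach AN ≤ 2 from baseline B, the reduction is 1 − 2/B.

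| Baseline AN | 5 | 8 | 10 | 20 | 30 |
|---|---|---|---|---|---|
| Reduction needed | 60% | 75% | 80% | 90% | 93% |

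In terms of AN reduction, the endpoint runs from between HiSCR50 and HiSCR75 to beyond HiSCR90, depending only on where the subject starts.

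**Illustration of prognostic strength (assumed model).** Let the Week 12 count be B × exp(shift + noise), rounded to whole lesions, with noise SD 0.9 and shift −1.0 on izokibep and −0.5 on placebo. Then P(AN ≤ 2) = Φ((ln(2.5/B) − shift) / 0.9).

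- Izokibep: 63% at B = 5 and 5% at B = 30.
- Placebo: 42% at B = 5 and 1% at B = 30.

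**Main simulation.** None of these inputs is in the documents:

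- Hurley II total of 100 or 150
- AN 0-2 rates of 20% v 40%
- baseline AN of 5 plus an overdispersed count with mean 4, 8 or 12
- between-subject SD of the log ratio of Week 12 to baseline count of 0.6, 1.0 or 1.5
- 25% with prior TNFi use

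These make 18 scenarios, with 1,500 runs each. The comparison was the CMH risk difference stratified by prior TNFi use against a logistic model with treatment, prior TNFi use and log baseline AN, standardised to the same marginal risk difference (computed as an augmented estimator with an influence-function SE). Variance ratios use the empirical spread of the estimates, so they do not depend on the standard-error formula.

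| SD of log ratio | Variance ratio, adjusted / CMH | Variance reduction |
|---|---|---|
| 0.6 | 0.78 to 0.92 | 8% to 22% |
| 1.0 | 0.88 to 0.97 | 4% to 12% |
| 1.5 | 0.94 to 0.99 | 1% to 6% |

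- The variance fell in all 18 scenarios. The largest reduction (ratio 0.778) is equivalent to 1/0.778 − 1 = 29% more subjects, and the smallest (0.992) to 1%.
- Power changed by −1 point (60.5% to 59.7%) to +9 points (78.1% to 87.1%). A mid-range case (n = 150, mean baseline AN 13, SD 1.0) went from 76.0% to 80.3%. Monte Carlo error is about 1 point per power figure.
- Under the null (n = 150, 3,000 runs), rejection was 6.0%, 5.2% and 5.7% for CMH and 6.0%, 5.2% and 5.8% for the adjusted estimator.

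**Effect of non-response imputation.** SAP 9.6.3 assigns failure, whatever the count, after relevant antibiotic use or when data are missing after discontinuation for an adverse event or lack of efficacy. This weakens the link to baseline. A second data model took 75 per arm, baseline AN log-normal with median 9 and log SD 0.6, truncated at 5, the shifts above, and noise SD 0.6 to 1.2. It gave about 6% to 16% lower variance and 2 to 6 power points. With an assumed 20% of subjects set to failure at random, this became about 5% to 13% and 2 to 5 points.

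**The case against.** The strongest objection is that nothing is wrong with the planned test. Under randomisation the stratified risk difference is unbiased, its standard error already covers chance imbalance in baseline AN, and it follows protocol 9.3.3, which calls for the same approach as the primary endpoint. Choosing a more efficient estimator could be called a matter of preference. The point about validity stands in full. It does not dispose of the efficiency point: the SAP uses this principle for its continuous endpoints, the data are already collected, and the marginal risk difference is preserved.

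The second objection is timing, and it also stands. SAP 4.1 says the document defines the final analysis, and SAP 8.6 refers to the Week 12 primary analysis in the past tense. Putting a more powerful estimator in place of a test in the hierarchy now would be a post hoc change to a confirmatory analysis.

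Third, the size is uncertain and can be close to nothing. That stands too: at SD 1.5 the variance gain is 1% to 6%.

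A reader might also infer three stronger points that the documents do not support:

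- Omitting Hurley Stage is not a fault. Everyone in this test is Stage II, so the factor is constant.
- Baseline counts are not ignored altogether. They are in the imputation model, and are absent only from the treatment comparison.
- Failure here does not undo most of the hierarchy. Only two tests follow in the SAP order.

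**Conclusion.** The point holds as a loss of precision. It is not a bias, an inflated error rate or an invalid test. The absolute threshold makes baseline AN prognostic unless subjects with high counts have proportionally larger reductions that offset it. The comparison nevertheless adjusts only for prior TNFi use.

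Under the stated assumptions the cost is roughly 1% to 22% of the variance and about −1 to +9 power points. It is smaller when response varies widely between subjects or when many subjects are imputed as non-responders. The upper end should not be read as the expected gain: it belongs to the lowest-variability scenarios, with no non-response imputation. The documents give no Hurley II number, baseline AN distribution or AN 0-2 rates with which to narrow the range.

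Nor do the documents support replacing CMH in this SAP's Week 12 hierarchy. The adjusted estimator could be the test only where it can be specified before Week 12 unblinding.

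**What to change.** Add to SAP 9.6.3 a risk difference obtained by standardisation from a logistic model with treatment, prior TNFi use and log baseline AN count, with a robust standard error, pooled by Rubin's rules over the same imputed datasets. Report a risk difference rather than a conditional odds ratio, so that the summary measure is unchanged.

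- **Week 12, this SAP:** keep CMH as the hierarchical test, and report the adjusted estimate beside it as supportive and labelled post hoc.
- **SAP 9.7, AN 0-2 at Weeks 4, 8 and 16:** use the adjusted estimator. These comparisons are descriptive and outside the alpha-preserving sequence. State that some Week 16 data had already been analysed when the change was made.
- **Where Week 12 is still blinded:** the adjusted estimator can be specified as the test itself, in the text corresponding to protocol 9.3.3.

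The cost is a paragraph of SAP wording, a short program, and a second estimator to explain alongside CMH. No new data are needed.

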#### Sixth secondary objective:

- Treatment: izokibep versus placebo
- Population of interest: subjects with HS who meet all inclusion/exclusion criteria and with baseline Hurley Stage II
- Variable of interest: achievement of AN count of 0, 1, or 2 at Week 12
- Summary measure: response rate, achievement of AN count of 0, 1, or 2 at Week 12 (Yes/No)
- ICE handling: treatment policy strategy, in general, with all subjects included in the analysis regardless of treatment discontinuation, concomitant medication/rescue medication, protocol deviations, or other actions. Subjects who receive antibiotic therapy that could affect HS will be included in the analysis by assigning non-response at subsequent timepoints. Multiple imputation and non-response imputation will be used to handle certain other types of missing data, analogously to the primary endpoint.

Seventh secondary objective:

- Treatment: izokibep versus placebo
- Population of interest: subjects with HS who meet all inclusion/exclusion criteria and have a baseline numeric rating scale (NRS)  $\geq 4$
- Variable of interest: change in NRS score after 12 weeks of treatment
- Summary measure: response rate, reduction in NRS scores, specifically, at least a 3-point reduction from baseline in NRS in Patient Global Assessment of Skin Pain at its worst, at Week 12 (Yes/No)
- ICE handling: hybrid estimand, with treatment policy strategy used for most ICEs and hypothetical strategy used to account for use of prohibited pain medications due to non-HS-related pain, when taken near a visit. All pain scores after such use of prohibited pain medication will be omitted from the dataset and replaced via multiple imputation in a model analogous to that used for multiple imputation of the primary endpoint. Multiple imputation and non-response imputation will be used to handle certain other types of missing data, analogously to the primary endpoint.

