	Intercurrent Event	Treatment policy strategy, in general, with all subjects included in the analysis regardless of treatment discontinuation, concomitant medication/rescue medication, protocol deviations, or other actions. Subjects who receive antibiotic therapy that could affect HS will be included in the primary analysis by assigning non-response at subsequent timepoints. Multiple imputation and non-response imputation will be used to handle

		certain other types of missing data, analogously to the primary endpoint.
	Population Level Summary	Response Rate of AN count of 0, 1, or 2 at Week 12 (Yes/No)
	Treatment Condition of Interest	izokibep versus placebo
	Population of Interest	Subjects with HS who meet all inclusion/exclusion criteria and have a baseline numeric rating scale (NRS) ≥ 4
	Variable of Interest	Change in NRS score after 12 weeks of treatment
Change in pain score from baseline in NRS Patient Global Assessment of Skin Pain at its worst at Week 12	Intercurrent Event	Hybrid estimand, with treatment policy strategy used for most ICEs and hypothetical strategy used to account for use of prohibited pain medications due to non-HS-related pain, when taken near a visit. All pain scores after such use of prohibited pain medication (within 28 days of start date of pain medication) will be omitted from the dataset and replaced via multiple imputation in a model analogous to that used for multiple imputation of the primary endpoint. Additional details of multiple imputation described in Section 9.6.4 . If prohibited pain medication is used for HS purposes, then any visit within 28 days of the start date of the pain medication will be imputed as NRI. Multiple imputation and NRI will be used to handle other types of missing data, analogously to the primary endpoint.
	Population Level Summary	Response rate, reduction in NRS scores, specifically, at least a 3 point reduction from baseline in NRS in Patient Global Assessment of Skin Pain at its worst, at Week 12 (Yes/No)

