If a subject received certain prohibited analgesic therapy within 28 days of the visit (including the day of the visit) for non-HS indication, the subject will have the pain scores after such use of prohibited pain medication omitted from the dataset due to the ICE and replaced via multiple imputation in a model analogous to the one used for the primary analysis. This process will only be done for the visit(s) within

28 days of the start date of the prohibited analgesic therapy for non-HS indication. For the multiple imputation, the model used will be analogous to the one for the primary endpoint, however the baseline NRS (at its worst) score will be added as a baseline covariate. In addition, the imputation will be done for the average NRS value for the visit.

Other missing data will be handled using multiple imputation analogously to the primary endpoint (including baseline NRS [at its worst] score as a covariate in the model).

Allowable and prohibited analgesics are pre-specified in sections 6.8.2.3 (Analgesic Therapy) and 6.8.3 (Prohibited Medications) of the protocol. A final list of all subjects who took prohibited analgesic therapy which results in NRI or data omission and subsequent multiple imputation will be created after the data is final and before unblinding and will include justification for choosing the subjects based on specific analgesic, timing relative to the visit, and other factors considered.

Since the NRS in Patient Global Assessment of Skin Pain is collected as a daily diary, the score used for analysis will be the average of the scores recorded 6 days prior to and the day of the visit (7 days total for the average). If scores are recorded on fewer than 3 of these 7 days, the pain score will be treated as missing; otherwise, the mean of the observed values (up to 7) will be used. The same approach to calculating the average value will be used for any visit occurring through Week 16 visit, including End of Treatment visits windowed to a visit on or before Week 16.

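### The pain endpoint's analgesic rule counts 28 days from the drug's start date, so a subject who started a prohibited analgesic before about Day 56 and still takes it at Week 12 keeps the observed score

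*SAP*

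**What the plan says.** The endpoint is a reduction of at least 3 points in worst skin pain at Week 12 among subjects with baseline NRS of at least 4. It is sixth in the SAP's secondary testing order (SAP 8.6).

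**HS use.** SAP 9.6.4 opens with the condition "If a subject received certain prohibited analgesic therapy within 28 days of the visit (including the day of the visit) for HS indication" and ends with the consequence "then the visit within the 28 days of the start date of the prohibited analgesic will be imputed as NRI". SAP Table 5 (6.8.1) states only the consequence: "then any visit within 28 days of the start date of the pain medication will be imputed as NRI".

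**Non-HS use.** SAP 9.6.4 uses the same opening condition, then confines omission and multiple imputation to visits within "28 days of the start date of the prohibited analgesic therapy for non-HS indication". Table 5 agrees: "All pain scores after such use of prohibited pain medication (within 28 days of start date of pain medication) will be omitted".

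**Everything else.** Table 5 sets the default: "Hybrid estimand, with treatment policy strategy used for most ICEs". A visit outside the 28 days keeps its observed score.

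**Protocol.** For prohibited analgesics taken for non-HS pain near a visit, Section 3 (seventh secondary objective) and Section 9.3.3 say: "All pain scores after such use of prohibited pain medication will be omitted from the dataset and replaced via multiple imputation". Neither gives a limit counted from the start date. For HS use the protocol states no non-response imputation (NRI) for analgesics; the SAP adds it.

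**Case list.** SAP 9.6.4 also provides for a final list of affected subjects, drawn up before unblinding and justified by drug, timing relative to the visit and other factors.

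**The concern.** The condition and the consequence in SAP 9.6.4 are different tests. The first asks whether the drug was taken recently. The second asks whether it was begun recently. They agree for short courses and part company for continuous use, which is the exposure most likely to be lowering pain at the visit. The visit score is an average of the daily scores over the 7 days ending on the visit day, so a drug taken through that week acts directly on the value analysed.

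As written, the rule imputes a subject who took the drug from Day 70 to Day 72 and keeps the score of one who took it from Day 50 through Week 12. Two programmers, one following the condition and the other the consequence, could produce different responder counts for an alpha-controlled endpoint. SAP 9.6.4 plans no sensitivity analysis that would show the difference.

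**Working it through.** The plan gives no sample-size figure, rate of prohibited use or subset size for the pain endpoint, so there is no stated figure to reproduce. The check is day arithmetic plus a range for the unknowns.

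**Inputs.** Week 12 is scheduled on Day 84, with an analysis window of Days 71 to 98 for mapped visits (SAP Table 1). Randomization is Day 1 and there is no Day 0 (SAP 6.2.1). The limit is 28 days from the start date (SAP 9.6.4 and Table 5).

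**Step 1: which starts are caught.** A start on Day s is caught at a visit on Day v if v − s ≤ 28, or if v − s + 1 ≤ 28 when the visit day is counted.

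- v = 84, elapsed days: first start caught is 84 − 28 = Day 56, so Days 1 to 55 escape.
- v = 84, visit day counted: first start caught is Day 57, so Days 1 to 56 escape.
- Over the mapping window, the first start caught moves from Day 43 or 44 (v = 71) to Day 70 or 71 (v = 98).

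**Step 2: two contrasting subjects, visit on Day 84.**

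| Course | Taken in the 28 days up to the visit? | Visit minus start | Handling under the consequence clause |
|---|---|---|---|
| Day 50, ongoing | Yes | 34 days | Observed score kept |
| Days 70 to 72 | Yes | 14 days | NRI (HS) or omitted and imputed (non-HS) |

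Both meet the opening condition of 9.6.4. Only the second is acted on.

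**Step 3: share of ongoing courses that escape.** Assume post-randomization starts spread evenly over Days 1 to 84.

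- If no course ever stops: 55/84 = 65%, or 56/84 = 67% with the visit day counted. This is the upper limit under even starts.
- If courses stop, those still active at the visit are mostly recent. With exponential durations of mean m (an assumption), each start e days before the visit has weight exp(−e/m). The escaping share is the sum over e = 29 to 83 divided by the sum over e = 0 to 83.
  - m = 14 days: 1.79/14.47 = 12%.
  - m = 28 days: 8.70/27.08 = 32%.

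**Step 4: weight of one subject.** The number with baseline NRS of at least 4 is not given. For an assumed 60 to 125 per arm, one changed status moves that arm's response rate by 100/60 = 1.7 to 100/125 = 0.8 percentage points.

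**Step 5: who changes status under an overlap rule.** For HS use, NRI can only turn a responder into a non-responder, so an escaping user without a 3-point drop is unaffected. For non-HS use, the observed score is replaced by imputed values, so status can move either way across imputations.

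**The case against.** **The opening condition and the blinded case list already cover this.** A continuing user meets the condition in 9.6.4, and the list allows timing to be considered. That is a partial safeguard, since a subject on a prohibited drug at Week 12 would be visible to the reviewers. But nothing says the list overrides the start-date limit, and for non-HS use the text says the process is done only for visits inside that limit. Table 5 does not contain the opening condition at all.

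**The exposed group is narrow.** Chronic non-HS pain and an expected need for opioids other than tramadol are exclusion criteria (Protocol 5.2, criteria 5 and 22), and Protocol 6.8.2.3 permits a range of analgesics. This stands, and it is the main reason to expect a small effect.

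**The endpoint is reached only if the primary and five earlier secondary tests succeed.** This also stands. The primary analysis is untouched.

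Three stronger readings are tempting, and the documents do not support them.

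- A reader might infer that two thirds of ongoing courses escape. That holds only if courses never stop.
- A reader might assume a rate of prohibited use and count every such subject as misclassified. The documents give no rate, and for HS use only those with a drop of at least 3 points change status.
- A reader might infer that the estimate departs from the protocol estimand for all prohibited use. The protocol's hypothetical strategy covers only non-HS pain. For HS use the observed score is consistent with the protocol's treatment policy, and the NRI is the SAP's own addition.

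**Conclusion.** The rule is wrong as written. For HS use, the fault is an inconsistency between the SAP's own condition and its consequence. For non-HS use, it is also an unlisted narrowing of the protocol: reading near a visit as 28 days is a reasonable way to make that phrase operational, but counting those days from the start date leaves out a subject taking the drug on the visit day.

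The size cannot be computed from the documents and is probably small. The gap affects only continuous use begun before about Day 56; a new course begun later is caught by its own start date. The escaping share rests on the assumptions of even starts and the stated durations. The direction of bias is also unknown: continuing use commoner on placebo would tend to dilute the difference, and commoner on izokibep to inflate it. The point is worth correcting because the endpoint is alpha-controlled and the present text allows two different responder counts.

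**What to change.** In SAP Table 5 and 9.6.4, replace the start-date limit with one window: any use of a prohibited analgesic, from start date to stop date or ongoing, that overlaps the 28 days up to and including the visit. Use the same test as both condition and consequence. Keep the present split, with NRI for HS use and omission with multiple imputation for non-HS use. State that the case list applies this rule. In SAP Section 5, list the remaining departure from the protocol, which omits all later pain scores for non-HS use.

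No new data are needed. Protocol 6.8 already requires start and end dates for every medication, and Protocol 6.8.2.3 has a daily analgesic diary through Week 16. The programming change is small, and a few more scores become NRI or imputed.

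Timing is the real cost. SAP 8.6 describes the Week 12 primary analysis in the past tense, so it appears to have been run. The change should therefore be documented in the clinical study report, as Protocol 9.3.1 requires for deviations made after the blind is broken. The corrected result should stand beside the result under the current rule, with the number of subjects by arm whose status changes.
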